10.3.2.4 Procedures and deadlines for notifying the sponsor

The investigator should initially complete a SAE reporting form (contained in the case report form). The investigator completes the SAE report form in the e-CRF, then validates, prints and signs the form before sending it by email; The form is then included in the patient's medical chart. In case of failure to connect to the e-CRF, the investigator should complete, sign and send the SAE report form to the safety Department. As soon as the connection is restored, the investigator must complete the SAE report form in the e-CRF.

Initial form must comprise:

- precise description of the case,
- SAE classification as expected or not
- SAE intensity
- SAE precise date of occurrence and resolution
- measures undertaken and treatments added
- whether the treatment was interrupted or not
- its evolution
- Causal relationship between the SAE and the investigational drug.
- Causal relationship between the SAE and the underlying condition/other treatments administrated.

Whenever possible, the investigator will provide the sponsor with any documents that may be useful for medical assessment of the case (medical reports, laboratory test results, results of additional exams, etc.). These documents must be anonymized. In addition, the investigator must state the study acronym and the number and initials of the study participant on each paper.

Any adverse event will be monitored until fully resolved (stabilisation at a level considered acceptable by the investigator or return to the previous state) even if the subject has terminated his participation in the trial.

The initial report, the SAE follow-up reports and all other documents must be sent to the sponsor's safety Department by mail ([contact]). It is possible to send the SAE to the AP-HP's Safety department by [contact]** only in case of unsuccessful attempt to send the SAE by e-mail. This is to avoid duplicated reports.

For trials which use e-CRF

- the investigator completes the SAE report form in the e-CRF, then validates, prints and signs the form before sending it by mail;
- In case of failure to connect to the e-CRF, the investigator should complete, sign and send the SAE report form to the safety Department. As soon as the connection is restored, the investigator must complete the SAE report form in the e-CRF.

The investigator must comply with all requests for additional information from the sponsor.

For all questions relating to an adverse event report, the safety Department can be contacted via email at [contact].

For cases of in utero exposure, the investigator will complete the "Notification and Follow-up form for a pregnancy occurring during participation in a study".

The investigator must monitor the pregnant woman throughout her pregnancy or until the pregnancy is terminated, and must notify the sponsor of the outcome of the pregnancy using this form.

If the outcome of the pregnancy falls within the definition of a serious adverse event (miscarriage, pregnancy termination, foetal death, congenital abnormality, etc.), the investigator must follow the procedure for reporting SAEs.

The initial pregnancy notification, the SAE follow-up reports, and any other documents will be sent to the sponsor according to the same procedures specified herein.

If it was the father who was exposed, the investigator must obtain the pregnant woman's permission before collecting information about the pregnancy.

10.3.3 Role of the sponsor

The sponsor, represented by its Safety Department, shall continuously, throughout the trial, assess the safety of each investigational medicinal product throughout the study.

10.3.3.1 Analysis and declaration of serious adverse events

The sponsor assesses:

- the **seriousness** of all reported adverse events,
- the **causal relationship** between these adverse events and investigational medicinal product and any other treatments,

All serious adverse events for which the investigator and/or the sponsor suspect a causal relationship with the investigational medicinal product are classed as suspected serious adverse reactions.

- the **expectedness assessment** of the serious adverse reactions

Any serious adverse reaction whose nature, severity, frequency or outcome is inconsistent with the safety information described in the investigator's brochure, is considered unexpected.

The sponsor, acting through its safety Department, assesses the expectedness of the serious adverse reaction based on the information described below.

- ❖ For serious adverse events likely to be related to the investigational medicinal product(s):
 - refer to the Investigator's Brochure

- ❖ For the serious adverse events likely to be related to blood samples : malaise, vomiting, pain, hematoma

The sponsor will report all suspected unexpected serious adverse reactions (SUSARs), within the regulatory time frame, to the ANSM (French Health Products Safety Agency)).

- The sponsor must send the initial report without delay upon receipt of the unexpected serious adverse reaction if it is fatal or life-threatening, or otherwise within 15 days from receipt of any other type of unexpected serious adverse reaction;
- The sponsor must provide all relevant additional information by sending follow-up reports, within 8 calendar days following receipt.

Any suspected unexpected serious adverse reaction must also be declared electronically using the Eudragilance European adverse drug reactions database managed by the European Medicines Agency (EMA).

The sponsor must notify all the investigators about any information that could adversely affect the safety of the trial subjects.

Special rules for double blind trials

After unblinding, if the administered product is the investigational medicinal product, the case will be immediately reported as suspected serious unexpected adverse reaction (SUSAR); however, if the administered product is the comparator, the unexpected nature of the adverse reaction will be re-assessed according to the reference document of the comparator found in the protocol.

10.3.3.2 Analysis and declaration of other safety data

This relates to any new safety data that may lead to a reassessment of the risk/benefit ratio of the trial or the investigational medicinal product, modifications in the investigational medicinal product use, the conduct of the clinical trial, or the clinical trial documents, or a suspension, interruption or modification of the protocol of the clinical trial or other similar trials.

The sponsor will inform the competent authority and the Ethics committee without delay after becoming aware of the emerging safety issue and, if applicable, describe which measures have been taken.

Following the initial declaration of emerging safety issue, the sponsor will declare to ANSM any additional relevant information about the new safety issues in the form of a follow-up report, which must be sent no later than 8 days after becoming aware of the information.

If the suspected unexpected serious adverse reaction meets the definition of an emerging safety issue, the sponsor will report both the SUSAR and the emerging safety issue to the ANSM according to the appropriate modalities and within the regulatory timelines as previously described.

10.3.3.3 Annual safety report

Not applicable taking into account the total duration of the research (5 months) less than 1 year.

10.3.4 Data Safety Monitoring Board (DSMB)

A DSMB will be set up for this trial by the sponsor. The DSMB must hold its first meeting before the first subject is enrolled and ideally before the protocol is submitted to the competent authority and the CPP (Research Ethics Committee). The DSMB's preliminary meeting will take place before enrolment, to define the frequency of committee meetings and safety data required.

All missions as well as the specific operating procedures of the DSMB are described in the study's DSMB charter.

The members of the DSMB are:

- 2 intensivists: Pr [name] (APHP, Sorbonne Université, Paris), Pr [name], Ulm university medical school, Germany)
- 1 methodologist : [name]

The DSMB will operate in accordance with the sponsor's procedures. The DSMB works in an advisory capacity only and the sponsor retains all decision-making authority.

The recruitment will be performed gradually, stopping temporarily inclusions after each step for DSMB analysis of safety data. Each analysis will be based on a CRF extraction of mortality, mortality during the first five days, serious adverse events, clinical worsening and biological tests (NFS, TP, TCA, Fibrinogen, creatininemia, liver tests (AST, ALT) during first 7 days.

11 DATA MANAGEMENT

11.1 Data collection procedures

During and after the clinical study, all data will be collected by the investigator and others specialised collaborators.

11.2 Identification of data recorded directly in the CRFs which will be considered as source data

Chest X-Rays results

11.3 Right to access data and source documents

11.3.1 Data access

In accordance with GCPs:

- the sponsor is responsible for ensuring all parties involved in the study agree to guarantee direct access to all locations where the study will be carried out, the source data, the source documents and the reports, for the purposes of the sponsor's quality control and audit procedures or inspections by the competent authority
- the investigators will ensure the persons in charge of monitoring, quality control and auditing or inspecting the interventional study involving human participants have access to the documents and personal data strictly necessary for these tasks, in accordance with the statutory and regulatory provisions in force (Articles L.1121-3 and R.5121-13 of the French Public Health Code)

11.3.2 Source documents

The source documents are any original document or item that proves the existence or accuracy of a data-point or fact recorded during the trial. Source documents will be kept by the investigator, or by the hospital in the case of hospital medical records, for the statutory period.

Document sources will be electronic medical records from both ICUs, laboratory tests results and imaging reports from La Pitié-Salpêtrière hospital facilities.

11.3.3 Data confidentiality

The persons responsible for the quality control of clinical studies (Article L.1121-3 of the French Public Health Code) will take all necessary precautions to ensure the confidentiality of information relating to the investigational medicinal products, the study, the study participants and in particular the identity of the participants and the results obtained.

These persons, as well as the investigators themselves, are bound by professional secrecy (in accordance with the conditions set out in Articles 226-13 and 226-14 of the French Criminal Code).

During and after the clinical study, all data collected about the study participants and sent to the sponsor by the investigators (or any other specialised collaborators) will be anonymized.

Under no circumstances shall the names and addresses of the participants involved be shown. The subject's initials will be recorded, along with an identification code specific to the study indicating the order of enrolment.

The sponsor will ensure that each subject has given written permission for any personal information about him or her which is strictly necessary for the quality control of the study to be accessed.

11.4 Data processing and storage of research documents and data

11.4.1 Identification of the data processing manager and location(s)

Data management and analysis of the data will be performed under the responsibility of the Clinical Research Unit of La Pitié-Salpêtrière hospital/Charles Foix by [name]. The data will be collected in the eCRFs by clinical study technicians and investigators.

11.4.2 Data entry

Non-identifying data will be entered electronically via a web browser, by the investigator in charge of the patient or a research technician.

11.5 Data ownership

AP-HP is the owner of the data. The data cannot be used or disclosed to a third party without its prior permission.

12 STATISTICAL ASPECTS

12.1 Description of statistical methods to be used including the timetable for the planned interim analyses

The statistical analysis will be performed by a biostatistician of the Clinical Research Unit of Pitié-Salpêtrière Hospital, under the responsibility of [name] [name].

Statistical analyses will be performed with the SAS® or R software with the most recent version at the time of the analysis.

Descriptive analysis will always be overall and by treatment group.

Unless specially mentioned, comparative analysis between groups will be systematically performed without adjustment (univariate analysis);

Flow chart

A flow chart according to the CONSORT recommendations will describe the recruitment and the follow-up of all study population.

Study population

The primary analysis of efficacy endpoints will be performed on all randomized patients for whom a baseline evaluation is available, on an intention-to-treat (ITT) population. All patients will therefore be analyzed in their initial randomization groups.

The safety set is defined as all randomized patients having received at least one dose of study treatment. Safety endpoints will be analyzed on the safety set.

Descriptive analysis

Qualitative variables will be described with frequency and percentage distributions, and quantitative variables with median, interquartile range, minimum and maximum values, mean and standard deviation.

Censored data will be described by Kaplan-Meier estimation or cumulative incidence function, with rate at D7 and D30 with 95% confidence interval.

Baseline characteristics

Demographical, clinical, biological and treatment characteristics will be described.

Primary analysis

The primary analysis will be performed in the intention to treat population.

The primary outcome is the change in EVLWi between D1 and day 7. These changes will be compared between both arms using analysis of covariance (ANCOVA), adjusted for the D1 EVLWi. This is fully equivalent to comparing EVLWi scores at D7 adjusted for the baseline EVLWi. Results will be expressed in terms of adjusted mean changes, with their 95% confidence interval. The unadjusted supportive analysis will be carried out by comparing EVLWi at day 7 between the two arms with a t test.

If the distribution of EVLWi is clearly incompatible with the ANCOVA or t test assumptions, then these analyses will be conducted on the ranks.

For patients dying before 7 days, the last thermodilution data will be retained for the primary analyses. If the patient's condition no longer warrants the presence of the transpulmonary thermodilution systems, then the catheter is removed before 7 days. In this case, the measurement of EVLWi can no longer be made, the last thermodilution data will be retained for the primary analyses. A sensitivity excluding those patients will be performed for analysing the primary endpoint.

Secondary analyses

For safety, the types and severity of AEs and SAEs will be described as frequency and percent by treatment arm. Fisher's exact tests will be used to compare the two treatment arms in terms of proportion of patients with death (all cause), at least one AE/SAE, at least one SAE. The number of these events (except death) will be compared between arms by Poisson regression.

Overall survival at D30 will be compared between the two groups using a logrank test.

The evolution of EVLWi during 7 days and other longitudinal repeated efficacy secondary outcomes will be compared between the two groups using a linear mixed effect model to take into account within subject correlation. If the model assumptions (normally distributed residuals with constant variance) is debatable, these analyses will be conducted on the ranks.

For other efficacy secondary outcomes, data will be described graphically and compared between arms by:

- chi2 test or fisher test for binary outcomes;
t-test or wilcoxon rank-sum test for quantitative variables.

Subgroups analyses will be performed according to :

- Presence of VV-ECMO at baseline (Yes/No)
- EVLWi at baseline (>10 ml/kg) (Yes/ No)

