3.2 Secondary objectives

Secondary objectives will be to test the hypothesis that FX06 infusion:

- improves mortality at 30 days following randomization
- reduces capillary leak (weight, fluid balance, systolic, diastolic, mean blood pressure, heart rate, catecholamine and lactate clearance)
- improves pulmonary recovery
- improves the evolution of organ failure
- reduces the need for hemodynamic support with catecholamines
- reduces the need for renal dialysis

The study will also determine

- the tolerance of FX06
- its pharmacokinetic
- PK/PD parameters of the drug
- Immunogenicity induced by the drug

Exploratory objectives will be:

- To characterize responder patients (defined as patient with a change in extravascular lung water index between D1 and Day 7 after inclusion > 30%)
- To study the prognosis (overall mortality) of responder patients (defined as patient with a change in extravascular lung water index between D1 and Day 7 after inclusion > 30%).

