5.6 Table or diagram summarising the chronology of the study

Actions	D1	D2 to D5	D6 to D7	D8, D10, D15, ICU discharge, death	D30	D60
Information	X					
Signature of the consent form from a close relative or surrogate, or emergency consent form	X					
Randomization	X					
Administration of study drug or placebo	X	X				
Pharmacokinetic study	X					
Medical history	X					
Clinical exam	X					
Co-infection or not	X	X	X			

Weight	X	X	X			
Fluid balance		X	X			
EVLWI measured by TPT (primary endpoint)		X	X			
Standard clinical monitoring	X	X	X			
Ventilatory settings	X	X	X	X		
Doses of catecholamines	X	X	X	X		
Arterial blood gases	X	X	X	X*		
Blood pregnancy test	X				X	
NFS, TP, TCA, fibrinogen, D-Dimers	X	X	X			
Electrolytes, creatinemia, serum glucose, CRP, LDH, NT-pro-BNP, procalcitonin, troponin	X	X	X			
ECG	X	X	X			
Liver tests	X	X	X			
Albuminemia	X	X	X			
SOFA score	X	X	X	X		
RRT or not	X	X	X	X	X	
TTE	X	X	X (D7)			
Chest X-RAY	X	X	X	X*	X*	
Adverse events		X	X	X	X	
Pursuit consent		X	X	X	X	
Vital status					X	
Withhold life-sustaining treatments decision					X	
Ventilator-free survival					X	
Secondary pneumonia, nb of episodes					X	
Rescue therapy with VV-ECMO					X	
Catecholamine-free days at D30					X	
RRT free days at D30					X	
Serum sample for immunogenicity and IL6 measurement			X (D7)			
Prescription of a highly effective method of contraception for three months (for women of childbearing potential)				X (ICU discharge)		
Patient's status						X

*, if clinically indicated

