6.4.4 Procedures for replacing participants

Subjects exiting the trial will not be replaced. They will receive further standard usual care, and their data will be analysed with intent to treat analysis according to their group of randomization.

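### Section 12.1 makes every efficacy endpoint, 30-day survival included, conditional on an undefined baseline evaluation and calls the resulting set ITT

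*Protocol*

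**What the plan says.** Protocol section 12.1 (Study population) defines two analysis sets.

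- **Efficacy:** the efficacy endpoints are analysed on "all randomized patients for whom a baseline evaluation is available, on an intention-to-treat (ITT) population". The sentence speaks of endpoints in the plural. Under Primary analysis the section adds: "The primary analysis will be performed in the intention to treat population".
- **Safety:** "The safety set is defined as all randomized patients having received at least one dose of study treatment".

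Survival has no set of its own. Section 12.1 (Secondary analyses) says only: "Overall survival at D30 will be compared between the two groups using a logrank test". The matching objective in section 3.2 is that FX06 "improves mortality at 30 days following randomization", so it is counted from randomisation.

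The statistical entry in the summary (section 1) announces an intention-to-treat analysis and attaches no baseline condition. Section 6.4.4 says of patients who leave the trial that "their data will be analysed with intent to treat analysis according to their group of randomization".

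The term baseline evaluation is not defined. Section 5.1 equates the baseline visit with the randomisation visit and Day 1, and within it asks for one thermodilution measurement, supine, before the first treatment. Treatment may start up to 12 hours after randomisation (sections 5.1 and 7.1.1).

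**The concern.** An ITT set holds everyone who was randomised. A set that also requires a measurement which may be taken after randomisation is a modified ITT set, and the protocol should call it that.

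A baseline value is understandable for the EVLWi analysis, which is a change from Day 1 adjusted for Day 1. Nothing similar applies to 30-day survival, ventilator-free survival, catecholamine-free days or RRT-free days. As worded, a patient without the baseline leaves all of these as well.

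What is at stake is the meaning and precision of the survival and organ-support results. Because the term is undefined, the membership of the efficacy set could also be settled after data have been seen.

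**Working it through.** **1. Which patients does each set hold?**

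| Set | Condition beyond randomisation | Used for |
|---|---|---|
| Efficacy (labelled ITT) | a baseline evaluation, undefined | EVLWi, D30 survival, ventilator-free survival, organ-support endpoints |
| Safety | at least one dose | AEs, SAEs, all-cause death by Fisher's exact test |

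A patient randomised without a baseline and then dosed is in the safety set only. A patient randomised without a baseline and never dosed is in neither. No defined set equals all randomised patients.

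**2. Two readings of the undefined term.**

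- *The Day 1 visit.* It is also the randomisation visit, so virtually every randomised patient has it and few or none are excluded.
- *The pre-dose Day 1 EVLWi.* This can be missing after randomisation. The reading must be supine and pre-dose, and the first dose must come within 12 hours. Section 7.4 encourages prone sessions of at least 16 hours when PaO2/FiO2 is below 150. A patient who is prone at randomisation could therefore pass the whole dosing window without a supine pre-dose reading.

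**3. The plan's own figure.** Section 12.2 gives a mean of 13.4, a 30% decrease, SD 5, two-sided 5% and 80% power.

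- Difference: 0.30 × 13.4 = 4.02 ml/kg.
- n per arm = 2 × (1.960 + 0.842)² × 5² / 4.02² ≈ 24.3, rounded up to 25. The stated 25 per group reproduces.
- Power at 25 per arm: 81.1% by the normal approximation (79.5% by the t distribution).

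**4. Primary endpoint if patients are excluded.** The documents give no rate, so these numbers are assumed (normal approximation).

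| Excluded per arm | Total N | Power |
|---|---|---|
| 0 | 50 | 81.1% |
| 1 | 48 | 79.5% |
| 2 | 46 | 77.8% |
| 3 | 44 | 76.0% |

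Section 12.5 expects no loss to follow-up, and the sample size carries no allowance for any.

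**5. Survival.** Apply the protocol's predicted mortality of about 60% (section 2.7.1) at 30 days; this use of the figure is an assumption. Expected deaths: 50 × 0.60 = 30.

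- If 5–10% lack a baseline (assumed): 2.5–5 patients, and 0.60 × 2.5 to 0.60 × 5 = 1.5–3 deaths removed.
- The standard error of a log hazard ratio with equal arms is about 2/√deaths. With 30 deaths it is 0.365; with 28.5 it is 0.375; with 27 it is 0.385. The ratios are √(30/28.5) = 1.026 and √(30/27) = 1.054, so the standard error widens by about 3–5%.
- Extreme case: all excluded patients are in one arm and all died. From 15/25 = 60%, that arm's mortality would read 14/24 = 58.3%, 13/23 = 56.5% or 12/22 = 54.5%. These are shifts of 1.7, 3.5 and 5.5 percentage points for 1, 2 or 3 patients. This is a bound and not an expectation.

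**The case against.** **The term may be harmless.** If baseline evaluation means the Day 1 visit, almost nobody is excluded. This stands as a limit on the size of the problem, and it rules out saying that patients will be dropped. It does not rescue the sentence, because the reader cannot tell which meaning applies.

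**Baselines should rarely be missing.** Sections 2.7.2 and 5.7 call thermodilution routine care, section 5.1 says the lines in use will be compatible, and section 6.2 excludes patients with a contraindication to the vascular access and moribund patients. This stands. A reader might take the need for special lines as a reason to expect many missing baselines, but the protocol points the other way. A reader might also rely on the schedule in section 5.6, where the row "EVLWI measured by TPT (primary endpoint") has no Day 1 mark. Section 5.1 requires that measurement explicitly, so the gap is a schedule inconsistency and not evidence that readings will be missed.

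**Section 6.4.4 is not in real conflict.** It deals with patients who exit, and section 12.1 also keeps patients in their randomised arm. Neither addresses a patient without a baseline. This stands; the inconsistency rests on the summary's unconditional ITT.

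**Deaths are counted elsewhere.** All-cause death is compared in the safety set, so a patient dosed without a baseline still counts there. This is right, and it answers the inference that these deaths vanish from the trial. It restores dosed patients only, and it does not repair the logrank test.

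**Selection would bias the comparison.** A reader might infer this from the idea that the sickest patients lack a baseline. The pre-dose measurement precedes blinded treatment, so whether it is missing should not depend on the arm. The shifts of 1.7–5.5 points need every exclusion to be a death in a single arm.

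**Conclusion.** The point holds as a defect of definition. Section 12.1 puts a baseline condition on all efficacy endpoints, leaves the condition undefined, and calls the result ITT, although the summary promises ITT without condition. Under the EVLWi reading this is a post-randomisation exclusion from endpoints that have no use for a baseline EVLWi, and no defined set contains all randomised patients.

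The size cannot be taken from the documents and is probably small. Under an assumed 5–10% missing and 60% mortality, the survival comparison loses about 1.5–3 of 30 deaths. Losing 1–3 patients per arm brings power on the primary endpoint from 81.1% to between 79.5% and 76.0%. The expected consequence is some loss of precision and a survival estimate for a selected group under the wrong label. The documents do not support a claim of systematic between-arm bias, nor a claim that exclusions are certain. The sample size of 25 per group is unaffected.

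**What to change.** In section 12.1:

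- Define ITT as all randomised patients, analysed in the arm assigned.
- Use it for 30-day survival, ventilator-free survival, the organ-support endpoints and every other endpoint that needs no baseline EVLWi.
- Define baseline evaluation. Restrict the baseline-available condition to the EVLWi change/ANCOVA analysis, and name that set modified ITT.
- State how a missing Day 1 EVLWi is handled. A single imputation made without regard to arm, such as the pooled mean baseline, is an acceptable option for patients with a later value, because baseline is independent of allocation. It is not essential to the correction. It cannot help a patient with no thermodilution at all, for whom the last-value rule has nothing to carry forward, so that case needs its own sentence.

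The cost is a few sentences of text. Data collection, sample size and randomisation do not change.
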